The design will be a prospective, open-label, multi-center longitudinal cohort study to assess the short- and long-term safety of FMT as well as the clinical resolution of diarrhea among 150 patients with 3 or more episodes of CDI (defined as 3 unformed stools over 24 hours for 2 consecutive days and either a positive stool test for CDI or pseudomembranes on colonscopy/sigmoidoscopy).²⁶ Subjects will be adult outpatients referred to one of the study centers after at least three recurrent episodes of CDI and previous treatment with at least one 10-day course of oral vancomycin or fidaxomicin. After FMT by colonoscopy/sigmoidoscopy or enema, patients will be followed prospectively and monitored for clinical resolution and adverse events at: 3 days (telephone), 6 weeks (clinical assessment), 6 months (telephone or clinical assessment), and 12 months (telephone or clinical assessment) after FMT. Subjects who recur will be offered a second FMT by colonoscopy with a different donor. Microbiome analysis will be conducted from stool samples at baseline and each of the 4 follow-up intervals.

III. Product Name/Chemical Structure

Fecal Microbiota Preparations

IV. Proposed Indication(s)

Recurrent Clostridium difficile infection

V. Dosage, Route of Administration and Dosing Regimen

V-A Colonoscopic/sigmoidoscopic FMT (FMP250)

Dosage Form: Screened human donor stool,

homogenized, filtered and aliguoted to sterile 250mL

vessels.

Route of Administration: Infusion will occur in the most proximal region of the colon that is technically feasible. The material will be infused through the working channel of the endoscope.

Dosing Regimen: 250 mL x 1 dose. In the event of a clinical non-response (defined in 'Protocol' Section), a repeat single 250 mL dose will occur from a different donor.

V-B Retention Enema FMT (FMP250E)

Dosage Form: Screened human donor stool,

homogenized, filtered

and aliguoted to sterile 250mL

vessels.

Route of Administration: Lubricated enema nozzle will be inserted into rectum and contents expelled into the distal colon with the subject requested to retain material for at minimum 30 minutes.

Dosing Regimen: 250mL x 1 dose. In the event of clinical non-response (defined in 'Protocol' Section), a repeat single 250 mL dose via colonoscopy will occur from a different donor.

4. [RESERVED, CFR 312.23]

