6. PROTOCOL

I. Study Overview and Specific Aims

The proposed multi-center, open-label, longitudinal cohort study aims to capture the safety profile of FMT in recurrent CDI, as well as to contribute additional efficacy data to the existing body of evidence. The proposed study includes collaboration with Investigators who are able to define the microbial landscape of patients pre- and post-FMT, and further elucidate if there is a microbial signature that predisposes patients to respond, fail treatment, or have adverse events from FMT.

Study Title

Safety of fecal microbiota **T**ransplantation: **O**penBiome **O**utcomes and **L**ongitudinal follow-up (STOOL) for recurrent *Clostridium difficile* infection

Specific aims (SA)

SA1. Determine the short-term (<6 weeks) safety of FMT for the prevention of further CDI recurrence.

Hypothesis: Careful donor screening for both infectious and non-infectious yet potentially microbiome-associated conditions minimize the risk of donor to recipient transmission of disease. Therefore, FMT will not be associated with meaningful number of *related* serious adverse events, recognizing that the recurrent CDI patient population is conventionally elderly with multiple comorbidities and may be at risk for FMT procedure-related complications compared to otherwise young and healthy individuals based on conventional literature.

SA2. Determine the long-term (6-12 months) safety of FMT for the prevention of further CDI recurrence.

Hypothesis: Careful donor screening for both infectious and non-infectious yet potentially microbiome-associated conditions minimize the risk of donor to recipient transmission of disease. Therefore, FMT will not be associated with meaningful number of *related* serious adverse events, recognizing that the recurrent CDI patient population is conventionally elderly with multiple comorbidities and may be at risk for developing new conditions, new medications or adverse events including death, but unrelated to FMT material.

SA3. Determine the longitudinal robustness of FMT clinical cure rate for the prevention of further CDI recurrence.

Hypothesis: We predict a clinical cure rate in keeping with the current literature (80-90%) at the12 month follow-up time interval. This predicted longitudinal response rate would exclude patients who require further antibiotics that put them at risk for CDI reinfection, not true recurrence.

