- Immunosuppressant medications
 - Current or recent (<3 months) treatment with anti-neoplastic agents
 - Current or recent (<3 months) treatment with calcineurin inhibitors (tacrolimus, cyclosporine)
 - Current or recent (<3 months) treatment with mycophenolate mofetil
 - Current or recent (<3 months) treatment with monoclonal antibodies to B and T-Cells, anti-TNF, glucocorticoids, antimetabolities (azathioprine, 6-mercaptopurine)
- Neutropenia with absolute neutrophil count (ANC) <0.5 x 10⁹/L
- Active gastroenteritis due to infectious cause other than CDI
- Short gut syndrome
- Colostomy
- Ascites
- End-stage liver disease
- Untreated, in-situ colorectal cancer
- Irritable bowel syndrome
- Inflammatory bowel disease including Crohn's disease and ulcerative colitis
- Microscopic colitis including collagenous colitis and lymphocytic colitis
- Severe food allergy (anaphylaxis) that cannot be confirmed as having been excluded from a donor's diet within the five days prior to donation
- Anorectal disorder/severe rectal sphincter tone abnormality or inability to retain enema material
- Unable or unwilling to tolerate colonoscopy/sigmoidoscopy, colonoscopy prep, or enema for any reason at discretion of MD
- Severe underlying disease that the patient is not expected to survive for the subsequent 12 months at the discretion of the MD.
- Any conditions for which, in opinion of MD, the treatment may pose a health risk

Target enrollment and rationale

The longitudinal cohort sample size (n=150) was chosen to allow recruitment in a suitable time frame. Strong consideration will be given to resubmitting documentation including IND amendment and IRB ammendment for a larger sample size and/or prolonged follow-up at the completion of the study.

III. Design Methodology

IV. Therapeutic Administration: Fecal Microbiota Transplantation Protocol

Donor selection, laboratory screening, and monitoring

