A. Donor Clinical Assessment: OpenBiome utilizes adult, healthy, universal donors who have given informed consent with oversight from Massachusetts Institute of Technology (MIT) IRB/COUHES. Refer to the OpenBiome Master File (BB-MF 15543) for donor selection details. An accompanying authorization letter from OpenBiome can be found in Appendix 1. The OpenBiome Donor Risk Factor Questionnaire (Appendix 2) is detailed elsewhere. Briefly, the Donor Risk Factor Questionnaire is modified from a similar questionnaire developed by the American Association of Blood Banks for blood donors. The stool donor questionnaire is used to exclude potential donors with infectious disease risk factors (eg. high risk sexual behavior, risk factors for variant Creutzfeldt-Jakob disease, high risk travel), medications that may mediate the microbiome, and a wide array of medical conditions that may have a theoretical link the microbiome.

B. Donor Laboratory Screening: Refer to the OpenBiome Master File (BB-MF 15543) for donor laboratory screening details. An accompanying authorization letter from OpenBiome can be found in *Appendix 1*. Briefly, both serologic and stool test are completed on prospective donors. All tests are outsourced to third-party Clinical Laboratory Improvement Amendments (CLIA)-certified testing facilities. As a condition for participation in this program, donors are required to submit written authorization for the disclosure of these test results to the OpenBiome, in compliance with the Health Insurance Portability and Accountability Act (HIPAA).

C. Donor Monitoring: Refer to the OpenBiome Master File (BB-MF 15543) for donor monitoring details. An accompanying authorization letter from OpenBiome can be found in *Appendix 1*. Briefly, the OpenBiome Donor Prospective Health Status Questionnaire (*Appendix 3*) details the routine questions asked before processing of a specimen, with initiation of clinical assessment by the Chief Medical Officer if a positive answer disclosed by a donor.

Subject preparation: determining eligibility, pre-treatment, and special considerations A. Subject Clinical Assessment

1. Potential subjects will undergo a medical interview to determine eligibility for the study and a physical exam will be performed at the screening visit.

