- Demographics: Age, sex, race/ethnicity
- Pre-existing medical conditions
- Concomitant medications
- Vital signs including height, weight, calculated body mass index (BMI)
- CDI History, including:
 - o Date of initial CDI diagnosis
 - Number of CDI recurrences since initial diagnosis
 - o Baseline clinical symptoms and severity related to CDI
 - CDI treatments received to date

Section 2: FMT Procedure

- Study patient identifier
- Date
- Description of FMT procedures, including:
 - Route of administration (colonoscopy/sigmoidoscopy or enema)
 - Location in colon where FMT delivered
 - Sedation (if applicable)
 - Prep quality (if applicable)
 - Findings of colonoscopy (if applicable)
- Dose
- Unit ID/Lot# of each treatment
- Expiration Date
- Storage Condition
- FMT retention time (if less than 1 hour)
- Immediate adverse events

2. Short-term assessment I (Day 3 – Telephone Assessment)

- Study patient identifier
- Date
- Any change in baseline clinical symptoms related to CDI
- Assessment of SAEs, including:
 - Any complications related to FMT administration
 - Any potential infectious complications such as transmissible enteric infections, sepsis, peritonitis, or bacteremia
 - Any non-serious newly diagnosed infections (specific organism and body site)

- Any new medical conditions / new medications with associated clinical course
- Any changes in pre-existing medical conditions with associated clinical course
- 3. Short-term assessment II (Week 6 Clinical Assessment)
 - Study patient identifier
 - Date
 - Vital signs including height, weight, calculated body mass index (BMI)
 - Any change in baseline clinical symptoms related to CDI including documentation of clinical cure or clinical non-response
 - Assessment of SAEs, including:
 - Any complications related to FMT administration
 - Any potential infectious complications such as transmissible enteric infections, sepsis, peritonitis, or bacteremia.
 - Any new non-serious diagnosed infections (specific organism and body site)
 - Any new medical conditions / new medications with associated clinical course
 - Any changes in pre-existing medical conditions with associated clinical course

4. Long-term assessment I (Month 6 – Telephone Assessment)

- Study patient identifier
- Date
- Self-reported height and weight, resulting calculated BMI
- Any recurrence of CDI with description of clinical course, including additional treatments received
- Assessment of any new SAEs

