- Any new medical conditions / new medications with associated clinical course
- Any changes in pre-existing medical conditions with associated clinical course

5. Long-term assessment II (Month 12 – Telephone Assessment)

- Study patient identifier
- Date
- Self-reported height and weight, resulting calculated BMI
- Any recurrence of CDI with description of clinical course, including additional treatments received
- Assessment of any new SAEs
- Any new medical conditions / new medications with associated clinical course
- Any changes in pre-existing medical conditions with associated clinical course

Data Analysis

Primary Study: Safety and Efficacy (Aims 1-3)

Safety endpoints will be collected with raw events and crude rates reported for overall cohort. Clinical cure rates will be calculated at each site. Both unweighted pooled clinical cure rates and weighted pooled clinical cure rates will be calculated with corresponding 95% confidence interval (CI) for overall study, as well as pre-defined

subgroups including: age, gender, modified Horn index, delivery modality, donor, retention time, site. Weighted pooled rates will be analyzed using the random effects model (DerSimonian-Laird method). Heterogeneity across sites will be assessed using the I² statistics and the Cochran Q test, where I² > 50% or Cochrane Q < 0.10 will be considered to indicate significant heterogeneity. Statistics will be performed using Stata SE 12.0 (StataCorp, College Station, TX).

Secondary Study: Microbiome (Aim 4)

DNA will be extracted from each frozen specimen collected from both donors and recipients. The V4 region of the 16S rRNA gene will be amplified using multiplexed bar-coded primers as previously described.²⁷ Up to 192 samples will be pooled onto a single lane of an Ilumina MiSeq for high-throughput sequencing. Quality trimmed and filtered sequence data will be clustered into Operational Taxonomic Units (OTUs) for computational analysis. Each recipient will receive an engraftment score based on their similarity (as quantified by the Jensen-Shannon Divergence) to the donor used in their FMT. Recipients will also be assessed for the long-term stability of their community and it's similarity to samples collected and previously published from both healthy and dysbiotic patients.

VI. Adverse Event Monitoring

We will capture both short and long-term safety profiles, including:

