1. Correlational Safety Data

• This open-label, longitudinal cohort will not have an untreated arm. Thus, it will be difficult to compare the probability of a newly acquired adverse event compared to a control. Given that the patient population with recurrent CDI tends to be older with core comorbidities, they are at high risk for new medical conditions, new medications, and poor outcomes, which may or may not be related to FMT. Thus, it is difficult to discern if there is an increased probability over baseline risk. This study has purposefully limited the age to 50 and designed exclusionary criteria (e.g. severe underlying disease that the patient is not expected to survive for the next 1 year) to reduce noise and strengthen any signal. Where possible age matched, prognostic factor matched population data will be considered to determine if FMT material may present a statistically significant increase in risk of developing a serious adverse event. However, this will not be the primary aim, and the focus will be on capturing count data/rates for serious adverse events.

2. Stool Collection

• Patients will be collect his or her own stool samples and there may be potential error carrying out this procedure. Our study minimizes this risk with clear instructions, simplified process, clear labels, significant contact with study representatives, and reminder phone calls.

XI. Investigator Credentials and Associated Body Contact Information

Principal Investigator:	[name] [name]
Address:	[name]
Co-Investigator:	[name] PhD
Address:	[name]
Co-Investigator:	[name] PhD
Address:	[name]
Co-Investigator:	[name] MD
Address:	[name]

Co-Investigator:	[name] MD
Address:	[name]
Co-Investigator:	[name] MD
Address:	[name]
Co-Investigator:	[name] MD
Address:	[name]
IRB Name:	MIT IRB/COUHES
IRB Address:	[name]
Principal Investigator CV:	Appendix 7

XII. ClinicalTrials.gov Requirements

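### The overall 95% intervals for cure have no term for donor, so they may be too narrow if outcomes correlate within donor

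*Combined protocol and SAP*

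**What the plan says.** Section 6.V, Data Analysis (Aims 1-3), plans the following for cure: "Both unweighted pooled clinical cure rates and weighted pooled clinical cure rates will be calculated with corresponding 95% confidence interval (CI) for overall study". The same intervals are planned for a list of subgroups that includes donor and site. The weighted rate uses DerSimonian-Laird random effects, and heterogeneity is assessed across sites with I² and Cochran's Q. The method for the unweighted interval is not named. No donor random effect, cluster-robust variance or test of between-donor heterogeneity appears.

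Safety is handled differently: "Safety endpoints will be collected with raw events and crude rates reported for overall cohort". Section 6.X, Potential Limitations, agrees: "the focus will be on capturing count data/rates for serious adverse events". Neither section plans a safety interval.

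On donors, section 6.IV says "OpenBiome utilizes adult, healthy, universal donors" and refers the details to a master file. Section 6.VII-D describes a donor pool, a stipend for each donation and rescreening every 60 days, which implies repeat donation. The size of the pool is not stated. On re-treatment, section 3.II says "Subjects who recur will be offered a second FMT by colonoscopy with a different donor". The procedure section of the case report form records "Unit ID/Lot# of each treatment".

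On sample size, section 6.II says "The longitudinal cohort sample size (n=150) was chosen to allow recruitment in a suitable time frame".

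**The concern.** Recipients of material from the same donor share an exposure, so their outcomes may be correlated. The plan allows for that possibility in several places. Donor is a cure subgroup, a second FMT uses another donor, and the microbiome engraftment score compares each recipient with the donor used. The storage study outlined in the section 7 addendum would match arms on donor and bowel movement. The interval for the overall cure rate does not reflect any of this.

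A subgroup table by donor would display differences between donors, but it leaves the width of the overall interval unchanged. At stake is whether the precision reported for the main efficacy estimate is right. For safety the issue is one of reporting: a crude count of material-related events does not show how many donors or lots lie behind it.

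**Working it through.** The plan states no interval width, power or precision target, so there is no figure to reproduce. The check starts from independence and then adds donor clustering.

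**Inputs from the documents.** n = 150 (section 6.II). Predicted cure is 80-90% (section 6.I, SA3). That prediction is for month 12; using its midpoint, 85%, for the 6-week rate is an assumption. Four initial sites are listed in section 6.VII-A.

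**Assumed inputs.** Donors: 5 to 50. ICC: 0.01 to 0.05 in the table, with higher values run as a check. Donors are used equally.

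**Step 1, independence.** Half-width = 1.96 × √(0.85 × 0.15 / 150) = 5.7 points. At 80% and 90% cure it is 6.4 and 4.8.

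**Step 2, donor clustering.** With m = 150 / donors, the design effect is DE = 1 + (m − 1) × ICC, and the half-width is multiplied by √DE.

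| Donors | m | ICC | DE | Half-width (points) |
|---|---|---|---|---|
| 5 | 30 | 0.01 | 1.29 | 6.5 |
| 5 | 30 | 0.05 | 2.45 | 8.9 |
| 10 | 15 | 0.01 | 1.14 | 6.1 |
| 10 | 15 | 0.05 | 1.70 | 7.5 |
| 20 | 7.5 | 0.01 | 1.06 | 5.9 |
| 20 | 7.5 | 0.05 | 1.32 | 6.6 |
| 30 | 5 | 0.02 | 1.08 | 5.9 |
| 50 | 3 | 0.02 | 1.04 | 5.8 |

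At ICC 0 nothing changes. With 30 to 50 donors and ICC up to 0.02, the width grows by a factor of at most √1.08 = 1.04.

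**Step 3, does the site random effect absorb it?** A beta-binomial simulation used a true cure rate of 85%, donors crossed with four near-equal sites and 6,000 runs per scenario. It gave these coverages for nominal 95% intervals:

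| Donors | ICC | Simple Wilson interval | DerSimonian-Laird over sites |
|---|---|---|---|
| 5 | 0 | 96.1% | 91.7% |
| 5 | 0.05 | 81.7% | 76.0% |
| 10 | 0 | 96.6% | 91.5% |
| 10 | 0.05 | 89.4% | 83.4% |
| 20 | 0.05 | 92.9% | 87.6% |
| 30 | 0.05 | 94.3% | 89.3% |

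Pooling over sites does not restore coverage. About 3.5 points of the DerSimonian-Laird shortfall are already present at ICC 0 and have nothing to do with donors.

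**Step 4, safety, for illustration only.** With zero events in 150 recipients, the two-sided exact upper 95% limit is 1 − 0.025^(1/150) = 2.4%. Replacing 150 by 150/DE at ICC 0.05 gives roughly 4.1% with 10 donors (effective n 88) and 5.8% with 5 donors (effective n 61). Zero affected donors gives 1 − 0.025^(1/10) = 30.8% for 10 donors and 16.8% for 20. Those last two figures concern the proportion of donors, which is a different quantity from the risk per recipient.

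**The case against.** The strongest reply is that no decision depends on the width. The sample size was set for feasibility, there is no success threshold or precision target, and the cure analysis is descriptive. Donor is not ignored either: its subgroup cure rates come with intervals, so large differences would be seen. One confirmed donor-to-subject transmission of a clinically concerning infection already triggers a safety review under section 6.VI-G, whatever any interval shows. All of this stands, and it keeps the point minor. It does not make the overall interval correct if donors differ.

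Three stronger readings are tempting, but the documents do not support them.

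- A reader might infer that intervals on material-related harm are too narrow. The plan has none; it reports counts and crude rates.
- A reader might infer that the pool is small, that each donor treats many subjects, and that the cure intervals are therefore probably too narrow. No pool size or ICC is given, and with a larger pool and a low ICC the effect is negligible.
- A reader might set the donor-level limit of 17-31% against the 2.4% for recipients as if the first corrected the second. It does not. Nor is the donor clearly the unit of risk: donors are questioned before each specimen is processed, and section 6.VI-F judges infection against an aliquot of the exact specimen given, so risk may vary by donation or lot.

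Modelling also has limits. With zero events, a donor bootstrap gives an interval of zero width and a donor random intercept is uninformative. For cure, about 22 failures (15% of 150) spread over 5 to 10 donors would estimate the donor variance poorly.

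**Conclusion.** The point holds for cure, conditionally. The overall 95% intervals have no donor term although donors are shared, and the step over sites does not supply one when donors are crossed with sites. The intervals may therefore be too narrow if cure correlates within donor. Over the assumed range the half-width could grow from 5.7 points by anything from almost nothing to about 3 points (8.9 − 5.7 = 3.2, with 5 donors and ICC 0.05).

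This rests on assumed donor numbers and ICCs, equal use of donors, and donors supplied across sites. That the planned intervals treat recipients as independent is itself inferred from the absence of a donor term, since the unweighted method is not named. For safety, what remains is a reporting gap rather than a faulty interval. Overall this is a worthwhile minor improvement.

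**What to change.** Keep all planned estimates and add to section 6.V:

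1. A sensitivity analysis giving a donor-clustered 95% interval for the overall first-FMT cure rate. Use either a donor random intercept crossed with site, reported as a population-averaged rate, or a cluster-robust variance with a small-sample correction. Assign each outcome to the donor of the first FMT.
2. The number of donors and the distribution of recipients per donor, reported with the cure results.
3. For material-related events, the number of donors and lots and the recipients per donor beside each count, listing both donors for subjects who had a second FMT. Do not fit a donor model to sparse or zero counts, and do not present a donor-level limit as a correction of the recipient-level rate.
4. The method for the unweighted interval.

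The cost is a few lines of SAP text and one extra model. The unit and lot identifiers are already recorded, and the planned donor subgroup already needs the link from unit to donor. The downside is a wider interval, and only an approximate one if donors turn out to be few.

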1. Colonoscopy/sigmoidoscopy: If patients experience clinical non-response and require vancomycin/fidaxomicin within 6 weeks post-FMT, after a 10 day course subject may opt to undergo a second FMT via colonoscopy with an alternate donor at the physician's discretion. Subjects will be followed per protocol for duration of study.

2. Enema: If patients experience clinical non-response and require vancomycin/fidaxomicin within 6 weeks post-FMT, after a 10 day course subject may opt to undergo a second FMT via colonoscopy with an alternate donor at the physician's. Subjects will be followed per protocol for duration of study.

Withdrawal

- 1. All reasons for study withdrawal will be reported.
- 2. Classification of withdrawal:
 - Post-enrollment but pre-FMT
 - Post-FMT but lost to follow-up at:
 - o Day 3
 - o Week 6
 - o Month 6
 - \circ Month 12
 - All reasonable efforts will be exhausted to contact subjects, and data analysis will be based on the last available assessment.
 - Adverse event or serious adverse event mediating withdrawal
 - Rescind informed consent
 - Procedure-related ineligible patients
 - Patients undergoing colonoscopy/sigmoidoscopy and discovered to be ineligible due to newly discovered exclusionary criteria (eg. in-situ colorectal cancer). FMT will not be performed as part of this study and no data will be collected.

V. Study Observations and Measurements

Study Endpoints

Safety Endpoints

Safety will be assessed by short and long-term safety summaries classified into:

- 1. Serious Adverse Events (SAE)
- 2. Adverse Events (AE)
- 3. New medical conditions
- 4. Changes in pre-existing medical conditions

Efficacy Endpoints

Efficacy will be captured through:

- 1. Clinical cure rate of first FMT at 6-week follow-up
 - Colonoscopy
 - Sigmoidoscopy
 - Enema

2. Clinical cure rate of second FMT at 6-week follow-up, in patients with clinical non-response

- Colonoscopy/sigmoidoscopy non-response: Alternate donor FMT by colonoscopy
- Enema non-response: Alternate donor FMT by colonoscopy

Microbiome Endpoints

Sequencing data targeting the composition of the gut microbiome will be used to assess whether there are consistent microbial signatures associated with clinical cure, clinical non-response, or safety endpoints.

Data Collection

Case Report Forms will be utilized to capture and collect data (Appendix 4):

1. Baseline Assessment (Day 0 - Clinical Assessment)

Section 1: Clinical Evaluation

- Study patient identifier
- Date

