For individual subjects enrolled in the study: any subject who has an SAE related to FMT will be ineligible for a second FMT during the course of the study.

FDA/CBER will be notified by phone or fax within 48 hours if the study is halted for review.

VII. Minimizing Risks to Human Subjects

VII-A. Human Subjects Involvement, Characteristics and Design

1. IRB approval for stool donor program has been obtained; Local site IRB approval from *each* study center will be obtained subsequent to required FDA approval of IND.

2. Subjects will be given informed consent using the standard consent process for colonoscopy/enema. Additional theoretical risk for transmission of infectious agents, and other diseases and conditions will also be discussed.

3. Donors will be given informed consent and will tested for most common infectious agents. Individuals with communicable disorders or a history of high-risk behaviors will not be permitted to donate.

4. Protections against risk are provided in detail below.

A sample size of 150 patients will be recruited. These patients will have been treated at or referred to one of the study centers for management of recurrent CDI.

Additional sites may be asked to join this study as needed to expeditiously achieve the targeted enrollment. The initial study sites will include:

1. Brown University and Women's Medicine Collaborative Providence, Rhode Island

2. Indiana University Health University Hospital Indianapolis, Indiana

3. University of Virginia Health Systems Charlottesville, Virginia

4. Edward Hospital Naperville, Illinois

This will be an open-label, longitudinal cohort study with follow-up at Day 3, Week 6, Month 6 and Month 12. The estimated duration of this study is 24 months. No patient will be excluded from recruitment on the basis of ethnicity, race, or disability. Subjects are expected to range in age from 18-75. Subjects will all be outpatients and will likely have comorbidities. All subjects will be fully informed about the purposes of the study, and risks and benefits of the study, and informed consent for all phases of the study will be obtained. Patients who agree to participate will be free to withdraw from the project at any time.

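### Site cure rates are pooled by DerSimonian-Laird with no stated scale, 0%/100% rule or few-site interval, so whether the 95% interval holds depends on choices the plan leaves open

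*Combined protocol and SAP*

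**What the plan says.** Section 6, V, Data Analysis (Aims 1-3) calculates cure rates by site and then pools them: "Both unweighted pooled clinical cure rates and weighted pooled clinical cure rates will be calculated with corresponding 95% confidence interval (CI"). This applies overall and within subgroups: "age, gender, modified Horn index, delivery modality, donor, retention time, site". For the weighted version, "Weighted pooled rates will be analyzed using the random effects model (DerSimonian-Laird method"). Heterogeneity is judged by I² and Cochran's Q, with no stated consequence for the pooled analysis. The software is Stata SE 12.0, with no command or option named.

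The text does not give the scale on which rates are pooled, the handling of a site with 0% or 100% cure, the interval method for either pooled rate, the meaning of unweighted (total cured over total treated, or the simple mean of site rates), or which rate is primary.

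Section VII-A lists four centres under "The initial study sites will include" and adds "Additional sites may be asked to join this study as needed to expeditiously achieve the targeted enrollment". On size, "The longitudinal cohort sample size (n=150) was chosen to allow recruitment in a suitable time frame". The efficacy endpoints are "Clinical cure rate of first FMT at 6-week follow-up", listed by colonoscopy, sigmoidoscopy and enema, and "Clinical cure rate of second FMT at 6-week follow-up, in patients with clinical non-response". Specific aim SA3 predicts 80–90% cure, stated for month 12.

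**The concern.** On the untransformed scale a site's variance is estimated as p(1−p)/n. At 80–90% cure, a site that does well by chance gets a smaller estimated variance and so more weight, which pulls the pooled rate up and narrows the interval. At 100% the variance is zero and the method cannot run without an added rule. Separately, DerSimonian-Laird with a normal interval treats the between-site variance as known, although four sites estimate it poorly.

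At stake is how a reader takes the Aim 3 result. A nominal 95% interval may cover well below 95%, and in small subgroups the point estimate itself can move by several points on a choice made after the data are seen.

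**Working it through.** The plan gives no power, precision or coverage figure to reproduce. The nominal 95% is the only benchmark.

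**Inputs from the documents.** N = 150 (Target enrollment), four initial sites with more possible (VII-A), cure 80–90% (SA3, here also used for week 6).

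**Assumptions.** Four sites of 38/38/37/37 or 75/40/25/10; eight sites of 18–19. True site rates are identical, or beta-distributed with SD 0.06.

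**Formulas.** With yᵢ the site estimate and vᵢ its variance, wᵢ = 1/vᵢ, Q = Σwᵢ(yᵢ − ȳ)², where ȳ is the w-weighted mean, and τ² = max{0, (Q − (k−1)) / (Σwᵢ − Σwᵢ²/Σwᵢ)}. Pooled estimate = Σyᵢ/(vᵢ+τ²) ÷ Σ1/(vᵢ+τ²). The normal interval is ± 1.96·SE. Hartung-Knapp uses a weighted residual variance and t on k−1 degrees of freedom.

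**Coverage of the mean over sites, %, at cure 80/85/90%** (simulation, Monte Carlo error 0.1–0.2 points):

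| Method | 4 identical, equal | 4 identical, unequal | 8 identical | 4 sites SD 0.06, equal | 4 sites SD 0.06, unequal |
|---|---|---|---|---|---|
| Untransformed, 0.5 at boundary sites only | 93.5/91.5/87.2 | 93.3/92.0/89.9 | 84.7/77.4/71.6 | 87.9/83.3/74.7 | 85.5/82.2/75.9 |
| Untransformed, 0.5 at every site | 95.4/95.2/95.0 | 95.2/95.0/94.8 | 93.8/92.3/86.5 | 90.0/87.8/84.3 | 87.7/85.8/82.3 |
| Untransformed, boundary sites dropped | 93.5/91.6/89.1 | 94.3/93.6/93.1 | 86.3/86.8/99.1 | 88.0/84.4/82.7 | 86.6/84.4/82.3 |
| Logit, normal interval | 96.8/96.7/96.3 | 96.7/96.3/96.2 | 95.9/94.8/92.3 | 93.1/92.6/91.9 | 90.9/90.0/89.2 |
| Double-arcsine, normal interval | about 96–97 | about 96–97 | 95.8/95.5/94.8 | 88–92 (both splits) | 88–92 (both splits) |
| Logit, Hartung-Knapp | 95.1/94.9/94.8 | 95.1/95.4/93.9 | 94.9/93.8/91.1 | 95.4/95.3/95.1 | 93.6/93.5/92.0 |
| x/N, Wilson | 95.0/96.2/96.0 | 94.9/96.2/95.9 | 94.8/96.3/96.0 | 85.2/85.4/81.6 | 81.3/81.5/77.0 |

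The bias of the first row is about +1 point at four identical sites and +2.2 to +2.6 points at eight.

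**Subgroups.** Three delivery modalities over four sites average 150/12 = 12.5 patients per cell. With 12 per site, the chance that at least one of four sites is at 100% is 1 − (1 − p¹²)⁴, which is 25%, 46% and 73% at 80%, 85% and 90% cure.

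Take 12, 11, 10 and 9 cured of 12 each. The crude rate is 42/48 = 87.5% (Wilson 75.3–94.1).

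- *0.5 at the 100% site.* Rates 12.5/13 = 0.962, 0.917, 0.833, 0.750; variances 0.0028, 0.0064, 0.0116, 0.0156. Q = 3.08, τ² = 0.0002, weights 0.523, 0.242, 0.135, 0.100. Estimate 91.2%, SE 3.98 points, interval 83.4–99.0.
- *100% site dropped.* Q = 1.34 on 2 df, τ² = 0, weights 0.511, 0.281, 0.208. Estimate 85.9% (74.7–97.0).
- *Logit, 0.5 at the 100% site.* Logits 3.22, 2.40, 1.61, 1.10; variances 2.08, 1.09, 0.60, 0.44; τ² = 0. Pooled logit 1.675, SE 0.434. Estimate 84.2% (69.5–92.6).

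The spread is 91.2 − 84.2 = 7.0 points from the same data and the same sentence of the plan. Untransformed pooling gives the corrected 100% site more than half the weight; logit pooling gives it 9%.

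**The case against.** A reader might infer that the planned interval under-covers even when sites are identical, and that adding sites makes it worse. The documents do not support either as a flat statement. They do not say untransformed and do not say normal interval. With 0.5 added at every site, untransformed pooling covers about 95% at four identical sites, and logit or double-arcsine pooling covers 96–97%. If sites at 100% are dropped and cure is 90%, coverage rises to 99% at eight sites. Eight sites is itself hypothetical, since VII-A only permits additions.

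The impact is also modest. The study is a single-arm cohort whose main objective is safety. No test uses the cure rate, and none of the triggers in VI-G does. Site rates and an unweighted pooled rate are reported beside the weighted one. The 12.5-per-cell figure is an average: modality is at the physician's discretion, and Section IX implies that not every site uses enema.

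All of this stands, and it limits the point. It does not reduce it to missing detail, for two reasons. First, once four sites differ by the assumed SD of 0.06, none of the normal-interval versions tested reaches 95%, including those that look sound with identical sites. Second, at eight identical sites and 90% cure, untransformed coverage is 72%, 87% or 99% according to a boundary rule that is not written down.

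**Conclusion.** The concern holds in conditional form, at minor to moderate severity.

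- **Identical sites:** four-site coverage of untransformed pooling with a normal interval is 87–94% or about 95%, depending on the boundary rule. At eight sites it is about 72–85%, 86–94% or 86–99% under the three rules.
- **Differing sites (four, SD 0.06):** untransformed 75–90%, double-arcsine 88–92%, logit 89–93%.
- **Small subgroups:** the estimate itself depends on the rule, by 7 points in the example.

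These figures rest on assumed site sizes, an assumed between-site SD, and use of the month-12 cure prediction at week 6. The second-FMT rate is affected only if it too is pooled this way, which the Data Analysis text does not clearly say. The heterogeneity rule compares Q itself with 0.10 where its p-value is meant; that is clerical.

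**What to change.** **Overall weighted rate.** Do not use untransformed DerSimonian-Laird with a normal interval. Pre-specify one of:

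- A logit or variance-stabilising scale with a Hartung-Knapp interval, and a 0%/100% rule where the scale needs one. Logit Hartung-Knapp covers about 92–96% at four sites; it is weaker with more, smaller sites (91–95% at eight identical sites).
- A patient-level logistic model with a random site intercept and a likelihood-based interval for the mean cure rate, if the named Stata version can produce it. This needs no boundary rule. It covers 97–98% with identical sites and 93.5–95% at SD 0.06, over four, six and eight sites.

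**Unweighted rate.** Define it as x/N or as the simple mean of site rates. If it is x/N with a Wilson interval, state that it describes the participating sites only: for a mean over sites at SD 0.06 and four sites it covers 77–85%. Name which rate is primary.

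**Subgroups, and second FMT if it would be pooled.** Report x/n with Wilson or exact intervals. This removes the bias and the boundary rule but does not improve coverage (about 90–93% for a mean over sites at SD 0.06). Give site results as site rates only.

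**Wording.** Refer to the p-value of Cochran's Q.

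**Cost.** Analysis text and code only. At four sites the overall half-width of 5.0–7.4 points (identical sites) grows by 2.5–2.7 points under logit Hartung-Knapp or 0.7–2.1 under the logistic model. At SD 0.06, 6.1–8.7 points grows by 4.5–6.2 or 1.2–4.3.
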